# 8.4.3 Intent-to-Treat (ITT) Population

All patients who are enrolled and allocated to treatment are included in the intent-to-treat population analysis.

# 8.4.4 Per-Protocol (PP) Population

Per-Protocol population will only include individuals who completed all four doses of OBP-301 and followed the study protocol

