#### 4.5 Stopping Criteria

#### 4.5.1 Patient Withdrawal Criteria

In accordance with applicable regulations, a participant has the right to withdraw from the study, at any time and for any reason, without prejudice to his future medical care.

Withdrawal from the study and therapeutic measures taken shall be at the discretion of the Investigator. A full explanation for the discontinuation from the study should be made in the participant's medical records and in the eCRF.

Premature discontinuation from active study participation may occur at any time due to any of the following reasons:

- Any situation where, in the opinion of the Investigator or the Medical Monitor, continued participation in the study would not be in the best interest of the patient.
- Positive pregnancy test (see Section for procedures to be followed in case of a pregnancy).
- Patient initiates other anti-cancer therapy. The anti-cancer therapy will be documented in the medical record and eCRF.
- Patient is unable or unwilling to comply with study procedures.
- Patient is lost to follow-up.
- Patient withdraws consent.
- Request by a Health Authority.
- Termination of the study by the study investigator(s).
- Progressive neoplastic disease, unless the Investigator feels this may be pseudoprogression, in which case the patient may remain on study until the next evaluation for extent of disease.

The reason(s) for premature study discontinuation/withdrawal should be reported in the eCRF and within the source documents along with the date of withdrawal. AEs should be documented according to Section 7.0 Adverse Events.

For all patients who discontinue, a Final Visit will be performed within  $28 \pm 5$  days after the last IP administration. If a participant is withdrawn because of an AE, the Investigator must arrange for the participant to have appropriate follow-up care until the AE is resolved or has stabilized. Unresolved AEs will be followed until the last scheduled follow-up visit or until the Investigator determines that further follow-up is no longer indicated. Investigators should attempt to collect the survival information as dictated in section 6.1.3.

Patients who discontinue the active study participation will not be replaced.

Any enrolled patients who are discontinued before study dosing will be documented as screen failures in the eCRF and replaced. No follow-up is required for these patients.

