# OBP-301

OBP-301 injection will be delayed for any ongoing Grade 3 toxicity attributable to OBP-301 at the time of the next scheduled injection. Patients who require a delay of OBP-301 injection of > 4 weeks (i.e., approximately 6 weeks from the previous injection) due to lack of resolution to

Grade 1 toxicity will be discontinued from the study. In this circumstance, the patient will be evaluable for toxicity, but will be replaced (up to the maximum enrollment) for efficacy assessment.

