# 6.1.2 Treatment Phase

Pembrolizumab infusions will be administered every 3 weeks  $\pm$  3 days until disease progression or patient is withdrawn for another reason. OBP-301 is to be administered prior to pembrolizumab in this patient population. All patients will receive OBP-301 at 2 x10^12 viral particles/ tumor injection administered every two weeks x 4 injection encounters. The tumor will be injected with OBP-301 four times (day 1, day 15, day 29, day 43). However, there may be some exceptions for OBP-301 injections which are outlined below.

- A. Up to 1 additional tumor injection encounter may be considered in discussion with the PI ([name]), which may be given 2 weeks after the 4th injection of OBP-301.
- B. Patients who initially respond to combination therapy may be rechallenged with OBP-301 at the time of disease progression, after discussion with the principal investigator.

Criteria for the additional single dose of OBP-301 is that the patient has not had disease progression and has had no grade 3 or 4 events related to OBP-301.

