# 6.1.4 Patient Withdrawal Criteria

In accordance with applicable regulations, a participant has the right to withdraw from the study, at any time and for any reason, without prejudice to his future medical care.

Withdrawal from the study and therapeutic measures taken shall be at the discretion of the Investigator. A full explanation for the discontinuation from the study should be made in the participant's medical records and in the eCRF.

Premature discontinuation from active study participation may occur at any time due to any of the following reasons:

- Any situation where, in the opinion of the Investigator or the Medical Monitor, continued participation in the study would not be in the best interest of the patient.
- Positive pregnancy test
- Patient initiates other anti-cancer therapy. The anti-cancer therapy will be documented in the medical record and eCRF.
- Progressive neoplastic disease, unless the Investigator feels this may be pseudoprogression, in which case the patient may remain on study until the next evaluation for extent of disease.
- An intercurrent illness or AE that requires concomitant medication that precludes further study participation
- Patient is unable or unwilling to comply with study procedures.
- Patient is lost to follow-up.
- Patient withdraws consent.
- Termination of the study by the Sponsor.
- Request by a Health Authority.

In addition, the Sponsor will discontinue a patient from active study treatment for any of the following criteria (subjects will continue to be followed as apprioprate for outcomes and toxicities:

- Patients who experience a Grade 4 hematologic toxicity or a Grade 3 or greater nonhematologic toxicity attributable to OBP-301 or the endoscopic procedure that has not resolved to Grade 1 (or basline) within 2 weeks of onset.
- OBP-301 injection will be delayed for any ongoing Grade 2 toxicity at the time of the next scheduled injection after consultation with the Principal Investigator. Patients who require a delay of OBP-301 injection of > 4 weeks (i.e., approximately 6 weeks from the previous injection) due to lack of resolution to Grade 1 toxicity will be discontinued from the study after consultation with Medical Monitor and Principal Investigator.

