# 8.5.2 Secondary Efficacy Endpoints

Secondary efficacy endpoints include the disease control rate, duration of response, progression-free survival (PFS), and overall survival (OS).

Duration of response is defined as the duration that subjects who have responded to combination therapy remain without disease progression.

Disease control rate is defined as the percentage of patients who have achieved complete response, partial response and stable disease.

Progression-free survival (PFS) is defined as time from registration to progression or death due to any cause. Progression is defined as radiologic progression of disease by RECIST v1.1 criteria.

Overall survival (OS) is defined as the time from registration until death from any cause,

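### The Per-Protocol set in Section 8.4.4 is a four-dose completer set: it drops patients who die or are stopped under the protocol's own rules, which builds guaranteed survival into OS and probably, though not certainly, raises the response rate

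*Combined protocol and SAP*

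**What the plan says.** Section 8.4 lists four analysis populations: Safety, Evaluable, Intent-to-Treat and Per-Protocol. Section 8.4.4 defines the last: "Per-Protocol population will only include individuals who completed all four doses of OBP-301 and followed the study protocol". The two conditions are joined and no exception is given. Section 6.1.2 plans injections on Days 1, 15, 29 and 43.

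Elsewhere the protocol provides for OBP-301 to end before the fourth injection:

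- **Progression.** Section 4.5.1 lists, among reasons for discontinuation, "Progressive neoplastic disease, unless the Investigator feels this may be pseudoprogression". Section 6.1.4 repeats it.
- **Unresolved toxicity.** Section 6.1.4 has the sponsor discontinue treatment for "Patients who experience a Grade 4 hematologic toxicity or a Grade 3 or greater nonhematologic toxicity attributable to OBP-301 or the endoscopic procedure" if it has not settled within two weeks of onset.
- **Long delay.** In Section 5.2.4, under OBP-301, "Patients who require a delay of OBP-301 injection of > 4 weeks" for lack of resolution to Grade 1 are taken off study.

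On the endpoints, Section 8.5.2 says "Progression-free survival (PFS) is defined as time from registration to progression or death due to any cause", and OS also runs from registration. Section 8.5.4 gives the methods for response and time-to-event endpoints without naming a population. The two-stage rule in Section 8.8 counts responders among 18 and then 37 evaluable patients.

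**The concern.** A per-protocol set is meant to show the result in patients whose treatment and follow-up agreed with the protocol. Here a patient whose injections were stopped because the protocol said so is left out. So is a patient who died before Day 43. The set selects on surviving and tolerating treatment up to dose 4.

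Two distortions follow. Time-to-event endpoints start at registration, while membership is settled only at dose 4, so members carry a period in which they could not have died. The response denominator also loses patients who probably did worse than average.

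The set is one of four listed populations and nothing limits it to a supportive role. A completer-only figure could therefore appear beside the main result under a label that readers take to mean adherence.

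**Working it through.** **1. The plan's own design (Section 8.8).** Inputs: null rate 15%, alternative 30%, 18 then 37 patients, continue with at least 3 responders, success with at least 9.

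P(success) = sum over x = 3 to 18 of Bin(x; 18, p) × P(Bin(19, p) ≥ 9 − x)

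This gives 0.0875 at p = 0.15 and 0.806 at p = 0.30, in line with the stated 10% and 80%. The design reproduces, and none of it depends on the Per-Protocol set.

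**2. Guaranteed survival in OS.** On schedule, dose 4 is 43 − 1 = 42 days after dose 1. The Schedule of Events footnote on OBP-301 timing requires at least 12 days between injections, so the shortest interval is 3 × 12 = 36 days. Time from registration to dose 1 adds to either figure.

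The documents give no survival assumption, so take an exponential with median m, timed from dose 1. Among patients alive at time L the median is m + L, with L = 42/30.44 = 1.38 months.

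| Assumed median (months) | Die within 42 days | Median among dose-4 survivors (months) |
|---|---|---|
| 4 | 21% | 5.4 |
| 6 | 15% | 7.4 |
| 10 | 9% | 11.4 |

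At 36 days L is 1.18, and the medians become 5.2, 7.2 and 11.2.

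**3. PFS.** The same shift cannot be applied. Progression in Section 8.5.2 is radiologic and the first scheduled on-study scan is at week 9 (Schedule of Events; Section 6.6.3), after Day 43. Section 6.1.4 also lets OBP-301 continue after apparent progression. Before dose 4, a PFS event is mainly a death or progression on an unscheduled scan, unless dosing is delayed past week 9. Deaths are excluded from the set with certainty; progressions are not.

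**4. Response rate.** With overall rate p, share d not completing four doses, and response rate q among them:

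Rate in completers = (p − d·q)/(1 − d)

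The documents give neither d nor q; the ranges below are assumptions.

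| True rate 15% | d = 10% | d = 20% | d = 30% |
|---|---|---|---|
| q = 0 | 16.7% | 18.7% | 21.4% |
| q = 7.5% | 15.8% | 16.9% | 18.2% |
| q = 15% | 15.0% | 15.0% | 15.0% |
| q = 30% | 13.3% | 11.2% | 8.6% |

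In counts, take a trial that just fails, 8/37 = 21.6%, with eight non-completers among the 37:

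- none responded: 8/29 = 27.6%
- one responded: 7/29 = 24.1%
- two responded: 6/29 = 20.7%
- three responded: 5/29 = 17.2%

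The direction reverses at two responders, since 8 × 8/37 = 1.7.

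**5. Chance of a completer rate at or above 9/37 (24.3%) when the true rate is 15%.** By simulation, for d = 10%, 20% and 30%:

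- q = 0, all 37 patients always enrolled: about 0.12, 0.21, 0.34
- q = 0, stage 1 rule applied: 0.11, 0.18, 0.28
- q = 7.5%, stage 1 rule applied: 0.08 to 0.09, 0.12, 0.17

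The comparison figure is the design's 0.0875. Inflation is clear at 20% to 30% non-completion and small or absent at 10%.

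**The case against.** The strongest reply is that no Per-Protocol result is planned. No section assigns an endpoint to the set, the decision rule uses evaluable patients, and Section 8.1 defers full detail to a statistical analysis plan. The Safety and Intent-to-Treat sets keep the stopped patients, and the Evaluable set has no dose requirement. All of this stands. It confines the point to the definition and use of a listed set, but it does not make the definition sound.

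A reader might go further and infer that every per-protocol response, PFS and OS figure is biased upward. The documents do not support that. For response, the direction depends on how non-completers fare: a responder stopped for toxicity leaves the numerator and lowers the rate. Patients who die before any scan are not in the Evaluable set either, so early death adds little to the difference between those two sets. For PFS, scan timing and permitted continued dosing make the protection partial.

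A reader might also infer that pembrolizumab adherence is ignored. The dose count covers OBP-301 only, but the second condition, following the protocol, can be read to cover the other drug.

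**Conclusion.** The point holds in limited form. Section 8.4.4 defines a completer set under a per-protocol name, and patients managed as the protocol directs fall outside it.

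- **OS from registration:** guaranteed survival to dose 4 follows from the definition, 42 days after dose 1 on schedule and at least 36. Its effect on the median, about 1.4 months on schedule, rests on an assumed constant hazard.
- **PFS:** upward bias is likely, of unknown size.
- **Response:** upward bias is likely, not certain. It needs non-completers to respond less often than completers. The shift from 21.6% to 27.6% assumes eight non-completers and no response among them.

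It would be tempting to conclude that the definition could turn a failed trial into a positive one. It cannot: success is judged on evaluable patients. The risk is a flattering supportive figure, which justifies a correction before analysis but does not threaten the primary conclusion.

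**What to change.** In Section 8.4.4 and the statistical analysis plan:

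1. Define Per-Protocol as eligible patients with no major protocol deviation, and list the major deviations before analysis. State that OBP-301 doses not given because of death, progression or a protocol-mandated stop are not deviations.
2. If a four-dose subset is still wanted, call it *four-dose completers*, label it supportive, describe its response rate as conditional on completion, and start its PFS and OS at a landmark at dose 4.
3. State in Section 8.5.4 which population each endpoint uses.

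One related conflict should be settled at the same time. Sections 4.5.1 and 6.1.4 say patients who discontinue are not replaced, while Section 5.2.4 says those stopped after a long toxicity delay are evaluable for toxicity "but will be replaced (up to the maximum enrollment) for efficacy assessment". These passages must be reconciled, because replacement could change who is counted among the 37.

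The cost is a few sentences, with no change to treatment, sample size or the decision rule. The downside is that the Per-Protocol figures will probably look less favourable.

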# 8.5 Efficacy Analysis

# 8.5.1 Primary Efficacy Endpoint

The primary efficacy endpoint will be the objective response rate (RR), as measured by RECIST 1.1 criteria.

Objective response rate is defined as the sum of partial responses plus complete responses as defined by RECIST v1.1 criteria.

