#### 6.6.3.2 Partial Response (iPR)\*

At least a 30% decrease in the sum of diameters of target lesions, taking as reference the baseline sum diameters.

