# 6.6.3.3 Progressive Disease (PD)\*

At least a 20% increase in the sum of diameters of target lesions, taking as reference the smallest sum on study (this includes the baseline sum if that is the smallest on study). In addition to the relative increase of 20%, the sum must also demonstrate an absolute increase of at least 5 mm.

Unconfirmed PD (iUPD) requires confirmation, which is done on the basis of observing either a further increase in size (or in the number of new lesions) in the lesion category in which progression was first identified in (ie, target or non-target disease), or progression (defined by RECIST 1.1) in lesion categories that had not previously met RECIST 1.1 progression criteria. However, if progression is not confirmed, but instead tumor shrinkage occurs (compared with baseline), which meets the criteria of iCR, iPR, or iSD, then the bar is reset so that iUPD needs to occur again (compared with nadir values) and then be confirmed (by further growth) at the next assessment for confirmed progressive disease (iCPD) to be assigned. If no change in tumor size or extent from iUPD occurs, then the timepoint response would again be iUPD.

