# 8.4.2 Evaluable Population

Any patient that has at least one radiographic assessment for response will be included in the Efficacy Population. Imaging studies preferably CT scan of the chest/abdomen/pelvis will be performed every 9 weeks as per the study schedule. Patients will be evaluated according to RECIST v1.1 criteria. Definitions of response evaluation are detailed in section 6.6 for further explanation. Only those patients whose response can be measured according to RECIST v1.1 will be included in this population.

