# 8.8 Determination of Sample Size

Sample size is determined according to Simon's two-stage Minimax design. We project a RR of 15% (historical RR for pembrolizumab alone), below which the combination regimen will be unacceptable, and a RR of 30% (expected RR rate for OBP-301 + pembrolizumab), above which the combination regimen will be considered worthy of further exploration. The null hypothesis that the RR is less than or equal to 15% will be tested against the alternative hypothesis that the RR is greater than or equal to 30%.

The sample size computations were performed assuming a 10% level of significance and 80% power. If 2 or fewer patients respond out of the first 18 evaluable patients, the study arm will be terminated and declared to have a negative result. If 3 or more patients respond out of the first 18 evaluable patients, enrollment will be extended to 37 patients. The treatment will be declared effective and worthy of further testing if 9 or more patients respond among the 37 patients entered. This two-stage design yields a  $\geq 0.80$  probability of a positive result if the true RR is  $\geq 30\%$ . It yields a  $\geq 0.90$  probability of a negative result if the true RR is  $\leq 15\%$ . A 95% confidence interval constructed around the expected RR of 30% can be estimated to be within  $\pm 14.8\%$  of the observed RR proportion. Assuming 10% are unevaluable/ineligible, we anticipate that a total of 41 patients will be enrolled in the study (assuming the study proceeds to the second stage).

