# **13 APPENDIX**

#### 13.1 ECOG performance status

Performance Status	Definition
0	Fully active, able to carry on all pre-disease performance without restriction.
1	Restricted in physically strenuous activity but ambulatory and able to carry out work of a light or sedentary nature, e.g., light housework, office work.
2	Ambulatory and capable of self-care but unable to carry out any work activities; up and about more than 50% of waking hours.
3	Capable of limited self-care, confined to bed or chair more than 50% of waking hours.
4	Completely disabled; cannot carry on any self-care; totally confined to bed or chair.

	RECIST 1.1	iRECIST
Definitions of measurable and non-measurable disease; numbers and site of target disease	Measurable lesions are $\geq 10$ mm in diameter ( $\geq 15$ mm for nodal lesions); maximum of five lesions (two per organ); all other disease is considered non-target (must be $\geq 10$ mm in short axis for nodal disease)	No change from RECIST 1.1; however, new lesions are assessed as per RECIST 1.1 but are recorded separately on the case report form (but not included in the sum of lesions for target lesions identified at baseline)
Complete response, partial response, or stable disease	Cannot have met criteria for progression before complete response, partial response, or stable disease	Can have had iUPD (one or more instances), but not iCPD, before iCR, iPR, or iSD
Confirmation of complete response or partial response	Only required for non- randomised trials	As per RECIST 1.1
Confirmation of stable disease	Not required	As per RECIST 1.1
New lesions	Result in progression; recorded but not measured	Results in iUPD but iCPD is only assigned on the basis of this category if at next assessment additional new lesions appear or an increase in size of new lesions is seen (≥5 mm for sum of new lesion target or any increase in new lesion non-target); the appearance of new lesions when none have previously been recorded, can also confirm iCPD
Independent blinded review and central collection of scans	Recommended in some circumstances—eg, in some trials with progression-based endpoints planned for marketing approval	Collection of scans (but not independent review) recommended for all trials
Confirmation of progression	Not required (unless equivocal)	Required

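### Sections 6.6.3, 8.5.1 and 8.8 define and count responders without a confirmation requirement, while the protocol's own appendix requires confirmation in a non-randomised trial

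*Combined protocol and SAP*

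**What the plan says.** **Primary endpoint (Section 8.5.1).** "Objective response rate is defined as the sum of partial responses plus complete responses as defined by RECIST v1.1 criteria". Confirmation is not mentioned.

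**Response definitions (Sections 6.6.3.1 and 6.6.3.2).** Partial response is "At least a 30% decrease in the sum of diameters of target lesions, taking as reference the baseline sum diameters". Complete response is likewise defined by what the scan shows. Neither section gives a repeat scan or a minimum interval. Section 6.6.4 speaks of confirming a complete response, but by sampling residual tissue, not by a later scan.

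**Progression (Section 6.6.3.3).** Here confirmation is written out: "Unconfirmed PD (iUPD) requires confirmation".

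**Evaluability (Section 8.4.2).** "Any patient that has at least one radiographic assessment for response will be included in the Efficacy Population".

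**Decision rule (Section 8.8).** "Sample size is determined according to Simon's two-stage Minimax design". The benchmarks are "We project a RR of 15% (historical RR for pembrolizumab alone") and "a RR of 30% (expected RR rate for OBP-301 + pembrolizumab"). The trial stops with 2 or fewer responders among 18 and is positive with 9 or more among 37, at a 10% significance level and 80% power.

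**Appendix table comparing RECIST 1.1 and iRECIST.** On confirming complete or partial response, the RECIST 1.1 column reads "Only required for non- randomised trials", and the iRECIST column refers back to RECIST 1.1. The opening of Section 6.6.3 directs the reader to this table.

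The governing criterion differs between places: RECIST 1.1 in Section 8.5.1, iRECIST in Section 2.1 and the Synopsis statistical paragraph. For this point it makes no difference, because the table gives the same confirmation rule for both.

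The documents do not say whether 15% and 30% are confirmed rates, when the stage 1 count is read, or how a response awaiting confirmation is treated at that look.

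**The concern.** Two careful readers can reach different counts from the same scans. Take a patient whose target-lesion sum falls by 30% at the first nine-week scan and has regrown by the second. A site working from Section 6.6.3.2 records a partial response. A statistician working from the appendix does not count it.

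The cut-offs are small whole numbers, so one such patient can decide whether the trial continues past stage 1 or is declared positive. If the rule is left open until data are in hand, the choice is made knowing which way it moves the result. That is a weakness in a primary endpoint with no concurrent control.

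The error rates in Section 8.8 also hold only if the responses counted and the 15% and 30% benchmarks are measured in the same way.

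**Working it through.** **Inputs.** From Section 8.8: n1 = 18, stop if X1 ≤ 2; n = 37 (19 more), positive if total ≥ 9; p0 = 0.15, p1 = 0.30. The share f of first responses that fail confirmation is not in the documents; it is assumed, over 0 to 25%.

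**Step 1: reproduce the stated design.**

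P(stop at stage 1) = P(X1 ≤ 2), with X1 ~ Bin(18, p).

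- At p = 0.15: 0.85^18 + 18(0.15)(0.85^17) + 153(0.15²)(0.85^16) = 0.0536 + 0.1704 + 0.2556 = 0.480.
- At p = 0.30, the same sum gives 0.060.

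P(positive) = Σ over x1 = 3 to 18 of P(X1 = x1) × P(X2 ≥ 9 − x1), with X2 ~ Bin(19, p).

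- At p = 0.15: 0.0875, so a negative result has probability 0.9125.
- At p = 0.30: 0.806.

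Both meet the limits in Section 8.8. An exhaustive minimax search with these inputs also returns 2/18 and 8/37. The design arithmetic is correct.

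**Step 2: find the slack.** Solving P(positive) = 0.10 gives p = 0.1542. The rule passes its 10% limit once the rate at which null patients are counted as responders exceeds about 15.4%. In terms of f: 1 − 0.15/0.1542 ≈ 2.7%.

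**Step 3: confirmed 15% benchmark, unconfirmed responses counted (both assumed).** The apparent null rate is 0.15/(1 − f).

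| f | Apparent null rate | P(positive) |
|---|---|---|
| 0 | 0.150 | 0.0875 |
| 5% | 0.158 | 0.112 |
| 10% | 0.167 | 0.144 |
| 15% | 0.176 | 0.184 |
| 20% | 0.188 | 0.236 |
| 25% | 0.200 | 0.300 |

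At f = 10% the expected count among 37 rises only from 37 × 0.15 = 5.6 to 37 × 0.167 = 6.2, about 0.6 of a patient.

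**Step 4: the other combinations.**

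- Benchmarks and count both confirmed, or both unconfirmed: no change (0.0875 and 0.806).
- Benchmarks unconfirmed, only confirmed responses counted: the rates become 0.15(1 − f) and 0.30(1 − f).

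| f | Rate under the alternative | Power | P(positive) under the null |
|---|---|---|---|
| 5% | 0.285 | 0.749 | 0.068 |
| 10% | 0.270 | 0.682 | 0.051 |
| 20% | 0.240 | 0.526 | 0.026 |

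At f = 10% the chance of stopping at stage 1 under the alternative rises from 0.060 to 0.099.

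**The case against.** The best defence is that confirmation already applies by reference. Section 8.5.1 defers to RECIST v1.1, the appendix summarises RECIST 1.1 as requiring confirmation in a trial of this kind, and Section 6.6.3 points to that appendix. This carries weight, and it rules out three stronger readings.

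- **That one unconfirmed scan makes a responder.** A reader might infer this because confirmation is spelled out for progression only. But progression is where iRECIST departs from RECIST 1.1, and the appendix lists response confirmation as unchanged. Silence on an unchanged rule is not a decision to drop it. Section 8.4.2 does not help this reading either: it sets the denominator, and one scan can make a patient evaluable without making that patient a responder.
- **That the 10% limit is lost.** Inflation needs a confirmed 15% benchmark and an unconfirmed count. The documents state neither, and f has no source in them. On a like-for-like basis the figure is 0.0875.
- **That stage 1 will be read on first scans, with a false futility stop of 0.10 to 0.24 instead of 0.060.** Those figures assume that 10 to 30% of true responses appear only at the second scan and that all 18 patients are judged on the first alone. The timing is unstated, and unless all 18 enrol within about nine weeks, the earlier patients will have later scans.

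Nor do the documents show that transient shrinkage is common. An injected lesion can be about 1 cm and is biopsied at each injection visit, and nothing bars it from being a target lesion. A 3 mm fall would be a partial response only if a 10 mm lesion were the sole target, and up to five are allowed.

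What remains is that a rule deciding the primary endpoint is left to a cross-reference, while the definitions that sites will use, and the sentence that counts responders, omit it.

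**Conclusion.** The point holds as a conflict over who counts as a responder. The operative sections carry no confirmation requirement, and the appendix imposes one under either criterion. The plan's sample-size arithmetic is sound.

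The effect on error rates is conditional. With a confirmed 15% benchmark and unconfirmed responses counted, the false-positive probability is about 0.14 if 10% of first responses fail confirmation and 0.30 if 25% do. It exceeds 0.10 once about 2.7% fail. With unconfirmed benchmarks and a confirmed count, the loss is in power instead: 0.682 at 10% failing. With matching bases nothing changes.

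This should be fixed before the stage 1 count is read. It is not a fatal flaw in the design.

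**What to change.** - **Sections 8.5.1, 8.8, 6.6.3.1 and 6.6.3.2, and the Synopsis statistical paragraph:** state that only a confirmed complete or partial response counts at both stages, that the next scheduled nine-week scan serves as confirmation, and that an unconfirmed response counts as a non-response. The patient stays in the denominator, so Section 8.4.2 need not change for this purpose.
- **Stage 1:** take the decision only when every response pending confirmation among the 18 has been resolved.
- **Benchmarks:** state in Section 8.8 that 15% and 30% are confirmed rates. If they are not, restate the power on the confirmed basis.
- **Reporting:** give the unconfirmed response rate as supportive.

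**Cost.** The change is to wording, and the existing scan schedule supplies the confirmation. Stage 1 may wait up to about nine weeks longer, and the reported response rate may be slightly lower. The sample size need not change if the benchmarks are confirmed rates. If they are unconfirmed, the stated 80% power no longer holds and the sponsor would have to accept the lower figure or revisit the design.
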